## 11.6 Stopping rules for safety

A Bayesian sequential monitoring rule will be implemented for safety. The stopping rule is defined as  $\Pr(\theta > \theta_T | \text{data}) > 0.8$ , where  $\theta$  denotes the proportion of toxicities (as defined in Section 11.5) and  $\theta_T$  denotes the expected serious toxicity rate for study treatments (set as  $\theta_T = 20\%$  for non-GVHD toxicity and  $25\%$  for GVHD toxicity). Interval analyses will be performed after every five evaluable patients (see 11.8 for patient evaluability). If the accumulated observed data suggests a high chance (i.e.,  $>80\%$  probability) for the “true” toxicity (as defined in Section 11.5) to be  $>20\%$  for non-GVHD events or  $25\%$  for GVHD events, enrollment will be paused and data for assessment of early stopping will be sent to QASMC for review to consider study termination. The following tables show the number of patients with the number of adverse events that would result in a pause of enrollment to assess premature stopping of the trial. The stopping boundaries were obtained using Multic99 version 2.1, a free-download software from M.D. Anderson Cancer Center (<https://trialdesign.org/one-page-shell.html#BTOX>). Specifically, we assume that the parameter  $\theta$  follows a prior distribution of beta (1,1), i.e.,  $\theta$  with mean = 0.5 but with relatively large variability (non-informative prior). Early stopping will be recommended if we observe 2 non-GVHD events out of the first 6 or 2 GVHD events out of first 5 patients, etc. (see Tables below), in patients treated in this trial. A simulation study is also performed to assess the operating characteristics for the above stopping rule (all scenarios are based on 10,000 simulated trials). For non-GVHD events, there will be only 15% chance to stop early if the “true” toxicity rate is 10%. In contrast, we will have 88% chance to stop early (with a median of 10 patients treated) if the “true” toxicity rate on flotetuzumab monotherapy is 30%. For GVHD events, there will be only 21% chance to stop early if the “true” rate is 15% and there will be 86% chance to stop early (with a median of 5 patients treated) if the “true” rate is 35%.

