**Stopping rules for non-GVHD toxicity:**

# Patients treated	5	10	15	20	25
Stop if the # Grade <math>\geq</math> 3 non-hematologic toxicity	2	3	4	5	6

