**Stopping rules for GVHD toxicity:**

# Patients treated	5	10	15	20	25
Stop if the # Grade <math>\geq</math> III aGVHD or severe cGVHD	2	4	5	6	8

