**11.8 Analysis Populations**

Safety analysis will include all patients who receive at least one dose of treatment drug.

Efficacy analysis will include patients who complete at least 1 cycle of treatment or patients who withdraw before completing Cycle 1 for a reason at least possibly related to drug toxicity.

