## APPENDIX I: Study-Specific DSM Tables

Protocol Objectives and Subject Evaluability	
Objective	# of patients evaluable for this endpoint to date
Primary	
To evaluate the efficacy of flotetuzumab in post-allo-HCT relapsed AML and MDS following Cycle 1 of flotetuzumab (Cycle 1 Day 28 assessment).	
Secondary	
To evaluate the efficacy of flotetuzumab monotherapy in post-allo-HCT relapsed AML and MDS following Cycle 2 (or following Cycle 1 for patients that receive only one cycle).	CR and CRi at C2D28 = ORR = MLFS = PR = SD = PFS = OS =
To evaluate the safety and tolerability of flotetuzumab +/- DLI in the post-allo-HCT setting	AEs = CRS and neurotoxicity = Acute GVHD = Chronic GVHD =

Interim Analysis and Early Stopping Rules
Does the study design include an interim toxicity analysis? No
Does the study design include an interim futility analysis? Yes
If yes, please insert text describing interim futility analysis from the protocol Fifteen patients will be enrolled in the first stage. This cohort will include patients who withdraw from the study for reasons unrelated to drug toxicity. If at least 2 CR/CRi are observed out of the 15 patients, then an additional 10 patients will be enrolled. If 6 or more CR/CRi are observed at the end of study, we would conclude that there is evidence of efficacy to warrant further investigation. There is less than 5% chance to stop the trial at stage 1 if the “true” response is 30% or higher. Conversely, there will be 55% chance to terminate the study early if the true rate is only 10% or less.
If yes, please provide data from the interim futility analysis when completed:
Are there early stopping rules that outline circumstances under which the study must be suspended or closed? Yes
If yes, please insert text describing early stopping rules from the protocol A Bayesian sequential monitoring rule will be implemented for safety. The stopping rule is defined as $\Pr(\theta > \theta_T   \text{data}) > 0.8$ , where $\theta$ denotes the proportion of toxicities (as defined in Section 11.5) and $\theta_T$ denotes the expected serious toxicity rate for study treatments (set as $\theta_T = 20\%$ for non-GVHD toxicity and 25% for GVHD toxicity). Interval analyses will be performed

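### The printed safety boundaries depart from the stated 0.8 posterior rule at four of ten looks, and the quoted stopping chances are those of the tables

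*Combined protocol and SAP*

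**What the plan says.** Section 11.6 defines the safety rule in full. With θ the toxicity proportion, the trigger is Pr(θ > θ_T | data) > 0.8, where θ_T is 20% for non-GVHD and 25% for GVHD toxicity, the prior is Beta(1,1), and looks come after every five patients. When the condition is met, enrolment is paused and the data go to QASMC.

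The section then turns to two tables: "The following tables show the number of patients with the number of adverse events that would result in a pause of enrollment". The table headed "Stopping rules for non-GVHD toxicity" prints 2, 3, 4, 5, 6 events at 5, 10, 15, 20 and 25 patients. The table headed "Stopping rules for GVHD toxicity" prints 2, 4, 5, 6, 8.

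Performance is introduced with "A simulation study is also performed to assess the operating characteristics for the above stopping rule", based on 10,000 simulated trials. For non-GVHD events the stated chances of stopping are 15% at a true rate of 10% and, at 30%, "we will have 88% chance to stop early (with a median of 10 patients treated"). For GVHD they are 21% at a true rate of 15% and 86% at 35%, with a median of 5 patients.

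Appendix I repeats the rule, the tables and these chances.

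**The concern.** The rule and the tables are both written as what triggers a pause, and the tables are presented as the output of the rule. If the tables are not that output, there are two triggers and no statement of precedence. At 4/15, 5/20 or 6/25 non-GVHD events, or 6/20 GVHD events, a team reading the table pauses and refers to QASMC, while a team computing the posterior carries on. That choice should not be made once the count is known. The quoted protection also belongs to only one of the two versions, so anyone applying the other would be relying on stopping chances it does not deliver.

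**Working it through.** **Inputs (Section 11.6):** cutoff 0.8 (strictly greater); θ_T = 0.20 and 0.25; prior Beta(1,1); looks at n = 5, 10, 15, 20, 25; printed boundaries as above.

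**1. Reproduce the quoted stopping chances.** I used exact binomial recursion: add five patients at a time, remove the probability at or above the boundary, carry the rest forward, and count a stop at any look including 25. For example, at look 1 for non-GVHD with true rate 0.3, Pr(at least 2 of 5) = 1 − 0.7⁵ − 5(0.3)(0.7⁴) = 1 − 0.168 − 0.360 = 0.472. Cumulative stopping over the five looks:

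| | 5 | 10 | 15 | 20 | 25 |
|---|---|---|---|---|---|
| Non-GVHD, 30%, tables | 0.472 | 0.669 | 0.775 | 0.840 | 0.882 |
| Non-GVHD, 30%, 0.8 rule | 0.472 | 0.669 | 0.703 | 0.757 | 0.805 |
| GVHD, 35%, tables | 0.572 | 0.651 | 0.760 | 0.838 | 0.857 |
| GVHD, 35%, 0.8 rule | 0.572 | 0.651 | 0.760 | 0.788 | 0.836 |

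| True rate | Stated | Tables | 0.8 rule |
|---|---|---|---|
| Non-GVHD 10% | 15% | 14.3% | 11.8% |
| Non-GVHD 20% | not given | 56.2% | 45.9% |
| Non-GVHD 30% | 88% | 88.2% | 80.5% |
| GVHD 15% | 21% | 21.1% | 20.0% |
| GVHD 25% | not given | 56.3% | 53.1% |
| GVHD 35% | 86% | 85.7% | 83.6% |

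The tables reproduce all four stated chances to within 1 point. With 10,000 simulations the standard error at 80.5% is √(0.805 × 0.195 / 10,000) = 0.4 points, so the 0.8 rule cannot have produced 88%. The GVHD 21% separates the two only weakly. The medians (10 and 5 patients) fit both versions and settle nothing.

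**2. Posterior at each printed boundary.** After x events in n patients, θ is Beta(1+x, 1+n−x), so

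Pr(θ > θ_T | data) = 1 − BetaCDF(θ_T; 1+x, 1+n−x) = Pr(Bin(n+1, θ_T) ≤ x).

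For 4/15 non-GVHD this is Pr(Bin(16, 0.20) ≤ 4) = 0.798.

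| n | Non-GVHD table | Posterior | Rule needs | GVHD table | Posterior | Rule needs |
|---|---|---|---|---|---|---|
| 5 | 2 | 0.901 | 2 | 2 | 0.831 | 2 |
| 10 | 3 | 0.839 | 3 | 4 | 0.885 | 4 |
| 15 | 4 | **0.798** | 5 (0.918) | 5 | 0.810 | 5 |
| 20 | 5 | **0.769** | 6 (0.892) | 6 | **0.744** | 7 (0.870) |
| 25 | 6 | **0.747** | 7 (0.869) | 8 | 0.820 | 8 |

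Four of the ten entries (bold) do not exceed 0.8. The one at 15 is a near miss; the other three are not rounding. Counting 0.798 as 0.80 gives 2, 3, 4, 6, 7, which stops 82.9% of the time at a true rate of 30%, still not 88%.

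**3. Which cutoff fits the tables?** With Beta(1,1), all ten entries need a cutoff of at least 0.7133 (the posterior at 3/10 GVHD, which must not stop) and below 0.7436 (6/20 GVHD, which must stop). Any value from about 0.714 to 0.743 works. At 0.8, several other priors, a beta-distributed historical rate and patient-by-patient monitoring were tried; none reproduced the printed boundaries together with the quoted chances.

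**4. How often does it matter?** This is the probability that the table is first crossed at a count below the rule's boundary. For non-GVHD at 30% it is 0.073 + 0.045 + 0.029 = 0.147 (looks 15, 20, 25). At 20% it is 13.9% and at 10% it is 2.7%. For GVHD only the look at 20 contributes: about 1%, 5.0% and 5.1% at true rates of 15%, 25% and 35%.

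**The case against.** The strongest reply is that the tables are the working rule. Their rows are worded as stop instructions, the text points readers to them, and nobody is told to compute a posterior. On that reading the simulated rule is the tabulated one, the quoted chances are right, and only the 0.8 is misstated. This is plausible, but Section 11.6 ties the pause directly to the 80% condition and never subordinates it to the tables. If the tables do govern, the published decision threshold is wrong, which still needs correcting.

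Several points of weight stand. Every discrepancy makes the table the more cautious version, and the consequence is a pause for review, not termination. The look at 25 falls at full planned accrual, when little enrolment remains to pause; leaving it out, the chance of a disputed non-GVHD count is 6.25% + 4.36% = 10.6% at a true rate of 20% and 7.29% + 4.47% = 11.8% at 30%. The GVHD effect is small.

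The example "Early stopping will be recommended if we observe 2 non-GVHD events out of the first 6" is not a plain slip. Two events in six give a posterior of 0.852 and two in seven give 0.797, so six is the last count at which 0.8 is exceeded if patients are checked one by one. That supports 0.8 as the intended cutoff, but six is not a scheduled look. Patient-by-patient monitoring from the fifth patient would stop 85.7% of the time at a true non-GVHD rate of 30%, which is not the quoted 88% either.

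**Conclusion.** The point holds. The stated 0.8 cutoff with a Beta(1,1) prior generates neither the printed boundaries at four of ten looks nor the quoted stopping chances, and no text says which version governs. The effect is moderate for non-GVHD toxicity (88.2% against 80.5% at a true rate of 30%; 56.2% against 45.9% at 20%) and small for GVHD (85.7% against 83.6% at 35%). These figures assume independent patients with a constant event rate, looks exactly at multiples of five, and a crossing at 25 counted as a stop; without that last look the tables reach only 84.0% at 30%, so the plan's 88% must include it. This should be fixed, but it does not undermine the design.

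**What to change.** State in Section 11.6 and Appendix I whether the rule or the tables govern, and make the other agree. The choice is the sponsor's.

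- **If the tables govern:** keep the printed counts and the quoted chances, and restate the cutoff as one value between about 0.714 and 0.743 with Beta(1,1).
- **If 0.8 governs:** reprint the four boundaries as 5/15, 6/20 and 7/25 (non-GVHD) and 7/20 (GVHD), and restate the chances as about 12% and 81% (non-GVHD) and 20% and 84% (GVHD). Review would then start one event later at those looks.

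Three smaller repairs belong in the same edit:

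- **Worked example:** bring the example citing six patients into line with looks every five, or state that monitoring is patient by patient and recompute the stopping chances.
- **Look trigger:** use one definition. Section 11.6 counts evaluable patients and points to Section 11.8, where "Safety analysis will include all patients who receive at least one dose of treatment drug". That agrees with the tables' count of treated patients, but Appendix I waits for completion of the first cycle.
- **Appendix I form:** the question "Does the study design include an interim toxicity analysis" is answered No, although the form goes on to reproduce the interim safety rule. Correct the answer.

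The cost is a text amendment in two places, with IRB approval as the Statement of Compliance requires. It adds no patients and no looks.

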**Stopping rules for non-GVHD toxicity:**

# Patients treated	5	10	15	20	25
Stop if the # Grade <math>\geq</math> 3 non-hematologic toxicity	2	3	4	5	6

**Stopping rules for GVHD toxicity:**

# Patients treated	5	10	15	20	25
Stop if the # Grade <math>\geq</math> III aGVHD or severe cGVHD	2	4	5	6	8

**11.7 Statistical analyses**

The data will be analyzed in both intent-to-treat (ITT) and per-protocol (PP) approaches. The ITT cohort will include all patients who have received at least one dose of flotetuzumab. The PP cohort will only include evaluable patients. Patients who withdraw before completing Cycle 1 for a reason unrelated to drug toxicity will not be evaluable for the primary objective and will be replaced. The data analyses will be descriptive in nature. Demographic and clinical characteristics of the sample, as well as response to treatment, and loss to follow up will be summarized using descriptive statistics. The CR rate, overall response rate, PR rate, SD rate, morphologic leukemia-free state (MLFS) rate, and AEs that occur during flotetuzumab monotherapy and their 90% confidence intervals will be presented. Rate of CR, overall response rate, PR rate, SSD rate, MLFS rate, and AEs with subsequent treatment will also be documented with exact 90% confidence intervals. Overall survival (OS) and progression-free survival (PFS) will be described using Kaplan-Meier product limit method.

**11.8 Analysis Populations**

Safety analysis will include all patients who receive at least one dose of treatment drug.

Efficacy analysis will include patients who complete at least 1 cycle of treatment or patients who withdraw before completing Cycle 1 for a reason at least possibly related to drug toxicity.

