## 1.4 Study Duration and Dates

It is generally expected that ~15-20 patients will be accrued per year. The target accrual for the study is 25 patients. Therefore, it is anticipated that the time from the study opening to completion of accrual will be ~18 months.

Patients will receive the investigational treatment for the first 28 days of the study (Cycle 1). Based on Day 28 response assessment, patients with CR/CRi/PR/SD may continue investigational treatment for another 28 days (Cycle 2); and patients with PD will come off study. All patients will be followed for 2 years after receiving investigational treatment.

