### 5.5 Definitions of Evaluability

Endpoint	To be evaluable for this endpoint, a patient must...
Efficacy (CR and CRi, C1D28 assessment)	Have completed all Cycle 1 infusions of flotetuzumab (or discontinued treatment due to drug toxicity or disease progression). Patients who are not evaluable for the primary objective will be replaced.
Efficacy (CR and CRi, C2D28 assessment)	Have completed all Cycle 1 and 2 infusions of flotetuzumab (or discontinued treatment due to drug toxicity or disease progression) and undergone C2D28 disease assessment
Efficacy (ORR defined as PR or greater)	Have completed all Cycle 1 infusions of flotetuzumab (or discontinued treatment due to

Efficacy (MLFS rate)	drug toxicity or progression) and undergone C2D28 disease assessment (or C1D28 assessment for patients who only received Cycle 1 treatment).
Efficacy (PR rate)	
Efficacy (SD rate)	
Efficacy (PFS)	
Efficacy (OS)	Have undergone any period of infusion of flotetuzumab
Safety and tolerability (AEs by CTCAE)	
Safety and tolerability (CRS and neurotoxicity by ASTCT)	
Safety and tolerability (acute GVHD by MAGIC criteria)	
Safety and tolerability (chronic GVHD by NIH severity score)	

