### 11.3 Sample Size Estimate

Twenty-five evaluable patients will be enrolled for this study. Assuming a single treatment arm compared to historical controls treated with chemotherapy alone or HMA monotherapy using a dichotomous endpoint of CR/CRi vs not CR/CRi (as defined by the Primary Endpoint, as above), based on Simon's Minimax two-stage design, we estimate a sample size of 25 patients would provide 80% power (alpha 0.05) to detect a difference between a 10% CR/CRi rate in historical controls treated with chemotherapy or hypomethylating agents alone (10, 11) compared to 30% CR/CRi rate in the treatment arm (effect size 20%).

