### 11.4 Stopping rules for futility

Fifteen patients will be enrolled in the first stage. This cohort will include all patients who have been treated, including those who withdraw from the study. If at least 2 CR/CRi are observed out of the 15 patients, then an additional 10 patients will be enrolled. If 6 or more CR/CRi are observed from this cohort of 15 patients, we would conclude that there is evidence of efficacy to warrant further investigation. There is less than 5% chance to stop the trial at stage 1 if the "true" response is 30% or higher. Conversely, there will be 55% chance to terminate the study early if the true rate is only 10% or less.

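### Section 11.4 ties the final cutoff of 6 CR/CRi to the first 15 patients instead of all 25, and the sections disagree on which patients enter the count

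*Combined protocol and SAP*

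**What the plan says.** **Design.** Section 11.3 describes a Simon minimax two-stage design for a CR/CRi rate of 10% against 30%, with alpha 0.05 and 80% power. It states: "Twenty-five evaluable patients will be enrolled for this study". Section 1.4 says: "The target accrual for the study is 25 patients".

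**Decision rule.** Section 11.4 enrols 15 patients, adds 10 if at least 2 respond, and then declares efficacy "If 6 or more CR/CRi are observed from this cohort of 15 patients". Appendix I repeats this text but applies the cutoff of 6 when the study ends.

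**Who counts.**
- Section 11.4, stage 1: "This cohort will include all patients who have been treated, including those who withdraw from the study". Appendix I says the stage 1 cohort includes withdrawals for reasons unrelated to drug toxicity.
- Section 5.5, to be evaluable for the primary endpoint: "Have completed all Cycle 1 infusions of flotetuzumab (or discontinued treatment due to drug toxicity or disease progression"; then "Patients who are not evaluable for the primary objective will be replaced".
- Section 11.7 plans both an ITT analysis (at least one dose) and a per-protocol analysis (evaluable patients). It adds: "Patients who withdraw before completing Cycle 1 for a reason unrelated to drug toxicity will not be evaluable for the primary objective", and replaces them.
- Section 11.8: "Efficacy analysis will include patients who complete at least 1 cycle of treatment or patients who withdraw before completing Cycle 1 for a reason". The only reason it goes on to accept is possible drug toxicity.

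**The concern.** There are two separate problems in the primary decision rule.

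The first is the denominator. Read as written, 11.4 judges success on the stage 1 cohort and never says what result among 25 patients counts as success.

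The second is the set of patients. A patient who leaves Cycle 1 for a reason unrelated to toxicity is counted at one stage and may be removed and replaced at the other. A patient who stops Cycle 1 for progression is evaluable under one section and has no place in another. The trial is open-label and single-arm, so if the plan does not fix the count in advance, the choice could be made after responses are known. Patients who leave early will usually have no documented CR/CRi at Cycle 1 Day 28, so removing and replacing them would tend to raise the observed rate.

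**Working it through.** **1. Reproduce the stated design.** Inputs from 11.3 and 11.4: n1 = 15, continue if at least 2 respond, n = 25, p0 = 0.10, p1 = 0.30. Try a final cutoff of 6 of 25.

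P(early stop | p) = P(Bin(15, p) ≤ 1).

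P(success | p) = Σ over x = 2 to 15 of P(Bin(15, p) = x) × P(Bin(10, p) ≥ 6 − x), where the last factor is 1 for x ≥ 6.

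| Quantity | Plan | Exact, 6 of 25 |
|---|---|---|
| Early stop at 10% | 55% | 54.9% |
| Early stop at 30% | under 5% | 3.5% |
| Type I error | 0.05 | 3.28% |
| Power | 80% | 80.17% |

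An exhaustive search for the minimax design with alpha ≤ 0.05 and power ≥ 0.80 returns this same rule. The sample size is right, and the cutoff of 6 belongs to 25 patients.

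**2. Section 11.4 taken alone.** P(Bin(15, 0.10) ≥ 6) = 0.22%. P(Bin(15, 0.30) ≥ 6) = 27.8%. Six of 15 is not the stated design.

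**3. Two patients traced through the sections.**

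| Treated patient who | 5.5 | 11.4 stage 1 | 11.7 per-protocol | 11.8 | Appendix I stage 1 |
|---|---|---|---|---|---|
| withdraws in Cycle 1, neither toxicity nor progression | out, replaced | in | out, replaced | out | in |
| stops Cycle 1 for progression | in | in | unclear | no clause | depends on whether this is a withdrawal |

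The 11.7 entry for progression turns on the word withdraw. Section 5.8 lists progression and withdrawal of consent as separate reasons for stopping. If withdrawal excludes progression, 11.7 agrees with 5.5. The gap in 11.8 and the whole first row remain.

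**4. What the choice of set could do.** The documents give no removed share d, so 5/10/20/30% is an assumed range. Removed patients are taken as non-responders unless stated.

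(a) Evaluable set at both stages, with the 10% null referring to all treated patients. The rate among evaluable patients is 0.10/(1 − d). At d = 0.10 this is 0.111, and the step 1 formula gives 5.1%.

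(b) All treated at stage 1 and evaluable at the end, the nearest to a literal combination of the sections, under the same null.

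(c) 25 treated patients without replacement, with the 30% target referring to evaluable patients. The rate is 0.30 × (1 − d). At d = 0.10 this is 0.27, and power is 69.9%.

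| d | (a) type I error | (b) type I error | (c) power |
|---|---|---|---|
| 5% | 4.1% | 4.0% | 75% |
| 10% | 5.1% | 5.0% | 70% |
| 20% | 8.2% | 7.6% | 57% |
| 30% | 13.4% | 11.6% | 43% |

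If 5% of removed patients respond, the rate in (a) becomes (0.10 − 0.05d)/(1 − d), and type I error is 3.7/4.1/5.4/7.3%. If removed patients respond at 10%, or if the 10% null refers to evaluable patients, it stays at 3.3%.

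(d) With replacement, 25 evaluable patients need on average 25/(1 − d) = 26.3/27.8/31.3/35.7 treated, against the accrual of 25 in 1.4.

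**The case against.** The cutoff wording is probably a drafting slip. Section 11.3 fixes 25 patients, 11.4 itself adds 10 after stage 1, and Appendix I places the cutoff at the end of the study. That stands. A reader might infer that the trial really has 27.8% power. The documents do not support this: 11.4 does not call fewer than 6 of 15 a failure, and it continues on 2. What it lacks is a success rule at 25.

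On the set, the text does lean one way for the final decision. Section 11.3 attaches the power statement to evaluable patients, 5.5 and 11.7 replace the rest, and with replacement only the evaluable count is fixed at 25. Appendix I is a reporting template that carries protocol text and is not an independent rule. Both points narrow the conflict. They do not remove it, because stage 1 in 11.4 expressly counts everyone treated and no sentence assigns the final count.

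Section 11.7 calls the analyses descriptive, plans both ITT and per-protocol results, and Appendix I tabulates replacements. Any divergence would therefore be visible. Visibility does not say which count decides.

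A reader might also infer that the evaluable set inflates type I error beyond 5%. That needs the 10% null to refer to all treated patients, which the documents do not say, together with an assumed removal share and low response among those removed. Early stoppers stay in follow-up under 5.8 and the marrow window is ±3 days, so a removed patient could be a responder. Because 5.5 keeps toxicity and progression stops in the set, the 20–30% rows are extreme under its definition.

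**Conclusion.** Two defects are established. Section 11.4 attaches the success cutoff to the wrong denominator; only at least 2/15 followed by at least 6/25 reproduces the stated 80% power, alpha 0.05 and early-stopping figures. The decision set is not the same across 5.5, 11.4, 11.7, 11.8 and Appendix I, and no sentence names the one that meets the cutoff. Neither finding rests on an assumption about dropout.

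The consequence of the set conflict is conditional. Type I error under the evaluable set lies between 3.3% (no effect) and 13.4% over the assumed range, according to the removed share, the response among removed patients and the population meant by the 10% rate. The documents fix none of these. They also do not show that the all-treated set is the only valid choice. Either set is defensible once it is named.

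**What to change.** 1. Change 11.4 so that efficacy requires at least 6 CR/CRi among all 25 patients at the end of the study.
2. Add discontinuation for disease progression to 11.8 and clarify 11.7 to match 5.5. Early progressors then count as non-responders unless CR/CRi is documented.
3. Name one decision set, used at both stages, in 11.4, 11.7, 11.8 and Appendix I. Report the other set as a sensitivity analysis.
4. State whether the 10% and 30% rates refer to evaluable or to all treated patients.

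The choice in item 3 is a trade-off for the sponsor:
- **Evaluable set as in 5.5.** This keeps the replacement rule, and keeps 3.3% and 80.2% if both rates refer to evaluable patients. Stage 1 in 11.4 and Appendix I would change, and 1.4 should say that the 25 are evaluable, because more will be treated.
- **All treated, no replacement.** This avoids possible upward bias and extends the stage 1 set in 11.4. It reverses the replacement rule in 5.5 and 11.7. If 30% refers to evaluable patients, power must be restated (about 75/70/57/43% over the assumed range).

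The cost is an amendment to the text. No new data are needed: early stoppers are already followed and both analyses are already planned.
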